4.1.11 Long-term Follow-up

Patients who discontinue treatment for any reason other than objective disease progression will continue to be followed with scans approximately every 12 weeks from the last tumor assessment until disease progression, or initiation of new anticancer treatment. If a patient discontinues treatment for a hematopoietic stem cell transplant, the frequency of imaging will be as per the transplant center standard of care.

After documentation of disease progression or start of new treatment, patients will be contacted by telephone approximately every 12 weeks for up to 12 months after the last dose of study drug to collect survival information.

4.2 Withdrawal of Patients from the Study

The duration of the study participation for each patient is defined as the time from the date of signed written informed consent through the completion of the follow-up period or withdrawal of consent.

4.2.1 Reasons for Withdrawal/Discontinuation

Patients may withdraw from the study at any time and for any reason without prejudice to their future medical care by the Investigator or others at the study site.

A patient may be withdrawn from treatment with ADCT-402 for any of the following reasons:

- Disease progression.
- AE.
- Withdrawal of consent.
- Major protocol deviation.
- Required treatment delay >21 days (except in case of potential patient benefit, which must be approved by the Sponsor).
- Following a dose delay due to toxicity, if the same toxicity recurs after second dose reduction, study drug must be discontinued permanently.
- Non-compliance, including lost to follow-up.
- Pregnancy.
- Other (e.g., development of contraindications with use of the study drug).
- The Investigator determines that it is in the best interest of the patient to discontinue the patient's participation in the study.
- Discontinuation of the study by the Sponsor.

- Death.

Patients experiencing other significant toxicities must be immediately and permanently withdrawn from treatment with ADCT-402 as follows:

- Any patient who experiences a Grade 3 or higher hypersensitivity ([Appendix 12.3](#)) reaction, regardless of premedication, during any cycle of treatment.
- Any patient who experiences a recurrent Grade 3 or 4 toxicity, excluding hematological toxicity.
- Any patient who requires a dosing delay >21 consecutive days from the planned Day 1 dosing at any time during treatment (except in case of potential patient benefit, which must be approved by the Sponsor).

4.2.2 Handling of Withdrawals

The Investigator will confer with the Sponsor if a patient experiences a serious or intolerable AE. If a patient discontinues from the study because of an AE, the patient will be followed to satisfactory resolution, until the Investigator deems the event to be chronic or not clinically significant, or until the patient is considered to be stable ([Section 6.3.2.6](#)).

For each patient who discontinues study treatment and withdraws from the study, the Investigator will record the reason(s) for discontinuation on the relevant page of the electronic case report form (eCRF). Whenever possible, each patient who discontinues study treatment will undergo an EOT visit and all EOT assessments ([Section 4.1.9](#)). Patients who fail to return for final assessments are to be contacted by the investigative site. Following a minimum of 2 documented unsuccessful telephone calls, the investigative site will send a registered letter to the patient in a final attempt to ensure protocol compliance.

Note: Once discontinued from the study, for any reason, patients are not permitted to be re-enrolled into the study.

4.2.3 Patient Replacements

Any patient in Part 1 who discontinues before completion of the first treatment cycle, for any reason other than a DLT, is to be replaced.

5 Study Treatments

5.1 Method of Assigning Patients to Treatment Groups

In Part 1 (dose escalation), patients will receive an IV infusion of ADCT-402 on Day 1 of each 3-week (21-day) cycle. The first patient receiving the first dose of ADCT-402 in the study must be observed for 7 days for occurrence of AEs prior to treating a second patient. The dose escalation procedure is described in [Section 3.2](#). If the highest allowed dose (300 µg/kg) is reached and the MTD is not identified, no further dose escalation will be allowed, pending a safety analysis and an amendment to the protocol.

In Part 2 (expansion), patients will be assigned to the recommended dose level(s) and schedule(s) of ADCT-402 identified in Part 1 by the DESC. Once the recommended Part 2 dose(s) and schedule(s) is/are determined, patients receiving lower or higher dose levels of ADCT-402 may be offered continued treatment at the recommended dose(s) and schedule(s).

5.2 Prophylactic Treatments for Hypersensitivity

If 1 patient experiences a Grade 2 or higher ([Appendix 12.3](#)) infusion-related hypersensitivity reaction at any time during Part 1 (dose escalation), all subsequent patients must receive prophylactic treatment, as described below or as per the institution's standard of care, to reduce the risk of hypersensitivity reactions.

- On Day 1 of each cycle, patients will be instructed to take 20 mg orally of dexamethasone at 12 and 6 hours before the start of ADCT-402 infusion. When necessary, 12 and 6 hours before the first infusion may be defined as “immediately before sleeping” and “immediately after waking up”.
- On Day 1 of each cycle, patients will be given 50 mg IV of diphenhydramine hydrochloride at 30 minutes before the start of ADCT-402 infusion.
- On Day 1 of each cycle, patients will be given 50 mg of ranitidine (or equivalent) IV at 30 minutes before the start of ADCT-402 infusion.
- For 2 days following administration of ADCT-402 on Day 1, all patients are to take dexamethasone 4 mg orally, twice per day.

Other medications for prophylaxis and treatment of hypersensitivity or infusion reactions may be administered, according to standard treatment center protocols. Medications for the treatment of severe hypersensitivity reactions, including anaphylaxis, should be available for immediate use.

If a patient experiences a Grade 1 or 2 hypersensitivity reaction ([Appendix 12.3](#)), the following medications (or equivalent) should be administered for 48 hours after ADCT-402 infusion:

- Ranitidine 150 mg orally, 2 times per day.
- Diphenhydramine hydrochloride 50 mg orally, 3 times per day.

Any patient who experiences a Grade 3 or higher hypersensitivity ([Appendix 12.3](#)) reaction should be discontinued from the study and immediately treated according to institutional

standard of care and determined by the treating investigator. These patients must be carefully observed after the treatment. Additional therapy, as per the institution's standard of care, should also be followed.

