3.1 Study Design

This is a Phase 1, open-label, dose escalation (Part 1) and expansion (Part 2) study of the safety and tolerability of ADCT-402, used as monotherapy, in patients with relapsed or refractory B-cell NHL. The study will determine the MTD, as well as evaluate the preliminary activity, PK, pharmacodynamics, and other exploratory assessments of ADCT-402.

Patients will receive a 1-hour intravenous (IV) infusion of ADCT-402, at escalating doses, on Day 1 of each cycle. If ADCT-402 is well tolerated after the first cycle, the infusion duration may be shortened to 30 minutes for subsequent cycles for that patient, at the Investigator's discretion.

For each patient, the study will include a screening period (up to 28 days), a treatment period (until withdrawal, [Section 4.2](#)), and a follow-up period to assess disease progression and survival for up to 12 months after the last dose of study drug. The total study duration will depend on overall patient tolerability to the study drug and response to treatment. It is anticipated that the duration of the entire study (Parts 1 and 2) could be approximately 3 years from first patient treated to last patient completed.

Part 1

In Part 1, patients will be assigned to treatment according to a 3+3 dose escalation design ([Section 3.2](#)) and oversight of a Dose Escalation Steering Committee (DESC) ([Section 6.3.1.1](#)).

During the conduct of Part 1, and prior to implementation of Amendment 5, alternative dosing schedules are being evaluated at the discretion of the DESC as described below:

- 120 µg/kg: Dosing every 3 weeks for 2 cycles. Patients with at least SD after the second cycle continue treatment at a reduced dose of 60 µg/kg q6weeks, beginning 6 weeks after Cycle 2 infusion.
- 150 µg/kg: Dosing every 3 weeks for 2 cycles. Patients with at least SD after the second cycle continue treatment at a reduced dose of 60 µg/kg q6weeks, beginning 6 weeks after Cycle 2 infusion.
- 200 µg/kg: Dosing every 6 weeks for 2 cycles. For patients with at least SD 6 weeks after Cycle 2, continue treatment at a reduced dose of 60 µg/kg q6weeks, beginning 6 weeks after Cycle 2 infusion.
- 200 µg/kg: Dosing every 6 weeks. For patients with at least SD 6 weeks after Cycle 1, continue treatment at a reduced dose of 60 µg/kg every 6 weeks beginning 6 weeks after Cycle 1 infusion.

Changes described in part 2 resulted from requests based on DESC decisions.

Part 2

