In Part 2, (expansion), patients will be assigned to the recommended dose level(s) and schedule(s) of ADCT-402 identified in Part 1 based on evolving safety, efficacy and pharmacokinetic data.

The *population* in Part 2 expansion may be restricted to specific histologies based on both signals of activity and the safety observed in Part 1.

Further, *dose levels and schedules* evaluated in Part 2 may include but are not limited to the following:

- A. **90, 120, 150, and/or 200 µg/kg:** Dosing every 3 weeks.
- B. **120 µg/kg:** Dosing every 3 weeks for 2 cycles. Patients with at least SD after the second cycle continue treatment at a reduced dose of 60 µg/kg q6weeks, beginning 6 weeks after Cycle 2 infusion.
- C. **150 µg/kg:** Dosing every 3 weeks for 2 cycles. Patients with at least SD after the second cycle continue treatment at a reduced dose of 60 µg/kg q6weeks, beginning 6 weeks after Cycle 2 infusion.
- D. **200 µg/kg:** Dosing every 6 weeks for 2 cycles. For patients with at least SD 6 weeks after Cycle 2, continue treatment at a reduced dose of 60 µg/kg q6weeks, beginning 6 weeks after Cycle 2 infusion.
- E. **200 µg/kg:** Dosing every 6 weeks. For patients with at least SD 6 weeks after Cycle 1, continue treatment at a reduced dose of 60 µg/kg every 6 weeks beginning 6 weeks after Cycle 1 infusion.

The continuation of each patient's treatment will be based on an independent verification of local response assessments, unless otherwise approved by the sponsor.

The DESC will determine and document the dose levels, schedules, and disease subtypes to be evaluated in Part 2. These determinations by the DESC will be provided in writing.

Based on emerging safety and efficacy profile, the DESC may add additional cohorts to part 2 of the study with the same or different dosing regimens and for the same or different B-cell NHL histologies. The dose will not exceed the highest dose tested in part 1 at which 3 patients cleared the DLT observation period.

Patients who discontinue treatment for any reason other than disease progression will continue to be followed approximately every 12 weeks from the last disease assessment until disease progression, or initiation of new anticancer treatment.

After documentation of disease progression or start of new treatment, patients will be followed (by telephone contact or chart review) approximately every 12 weeks for up to 12 months after the last dose of study drug to collect survival information.

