5.4 Dose Delays and Modifications

The Investigator may suspend ADCT-402 dosing for up to 21 days for any patient who experiences a protocol-defined DLT after Cycle 1 (the defined DLT observation period). At the discretion of the Investigator, the dose may also be delayed for up to 21 days for any toxicity that does not meet DLT criteria. Resumption of dosing with ADCT-402 after suspension is at the discretion of the Investigator, based on assessment of the patient's clinical condition and whether or not the patient is deriving potential clinical benefit from treatment with ADCT-402. Following recovery to Grade 1 or to baseline grade, treatment with ADCT-402 may resume at the Investigator's discretion.

Patients who resume treatment following a dose delay may, at the discretion of the DESC, have their dose of study drug reduced by 50%. If toxicity occurs again at the reduced dose, the patient will be discontinued from the study.

During part 2, dose delay due to toxicity may extend beyond 21 days at the discretion of the investigator, in consultation with the Sponsor, based on assessment of the patient's clinical condition and whether or not the patient is deriving potential clinical benefit from treatment with ADCT-402. When dosing is resumed, the dose may be decreased by 50% at the discretion of the Investigator, in consultation with the Sponsor.

If the dose is reduced and the toxicity recurs, the dose will be further reduced by 50%.

If toxicity recurs after second dose reduction, study drug must be discontinued permanently.

If dose is held for six weeks or more, restaging scans must be done prior to restarting dosing to rule out disease progression.

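### For Grade 3 or higher hypersensitivity, Protocol 5.2 takes the patient off the study while 4.2.1 stops only ADCT-402: a minor wording error that, followed literally, could end follow-up

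*Protocol*

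**What the plan says.** Two sections of the protocol give an instruction for the same event, Grade 3 or higher hypersensitivity.

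- Section 5.2 (prophylaxis): a patient with such a hypersensitivity "reaction should be discontinued from the study and immediately treated according to institutional" standards.
- Section 4.2.1 (withdrawal): the patient "must be immediately and permanently withdrawn from treatment with ADCT-402 as follows", and the first item listed is this "reaction, regardless of premedication, during any cycle of treatment".

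Section 5.4 has two rules on recurrent toxicity. The first reads "If toxicity occurs again at the reduced dose, the patient will be discontinued from the study". The text that follows the Part 2 paragraph reads "If toxicity recurs after second dose reduction, study drug must be discontinued permanently".

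Other sections bear on what was meant:

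- Section 4.2 defines participation as running from consent "through the completion of the follow-up period or withdrawal of consent". Toxicity is not named as an end point.
- Section 3.1 plans "a follow-up period to assess disease progression and survival for up to 12 months after the last dose of study drug" and adds: "Patients who discontinue treatment for any reason other than disease progression will continue to be followed approximately every 12 weeks". Section 4.1.11 repeats this and specifies scans, with telephone contact for survival once the patient progresses or starts new treatment.
- Section 4.2.2 treats stopping study treatment and withdrawing from the study as separate steps, and bars re-enrolment after study discontinuation. It secures AE follow-up and, where possible, the end-of-treatment (EOT) visit. It does not mention later scans.

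**The concern.** Stopping a drug and leaving a study are different acts in this protocol, and leaving cannot be reversed. An investigator handling a severe reaction is likely to turn to 5.2, which gives the study-exit instruction without pointing to the follow-up in 4.1.11. The first rule of 5.4 has the same gap.

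If a site took either sentence at face value, disease assessment and survival contact could stop because of toxicity. That kind of loss may be informative. The data exposed are those behind PFS, OS and, in responders, duration of response.

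**Working it through.** The plan states no figure to reproduce. The check is a comparison of wording, followed by the visit windows and the SAP rules.

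**1. Is the conflict like for like?** For 5.2 against 4.2.1, yes: same event, same grade, different action. Within 5.4, no: the first rule is triggered by recurrence at a reduced dose, the later one by recurrence after a second reduction. Section 5.4 therefore shows the same loose wording but is not a second contradiction.

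**2. Would another visit supply a scan after a reaction and stop on Cycle 1 Day 1?**

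Inputs:
- Screening scan: up to 28 days before Day 1 (4.1.1).
- EOT visit: within 30 days (4.1.9; schedule 12.1.1, note 25).
- EOT scan, if progression is not already documented: required only when the last assessment was more than 9 weeks earlier, i.e. 9 × 7 = 63 days (4.1.9).

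Longest interval = 28 + 30 = 58 days. Since 58 < 63, with a margin of 5 days, the EOT scan is not triggered. The 12-week visit is a PK and ADA blood sample (4.1.10); the schedule marks survival and new-treatment information there but no disease assessment. The next scheduled scan is the first one under 4.1.11, due 84 days after the screening scan: 84 − 28 = 56 to 84 − 1 = 83 days after the dose.

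**3. How far does the 58-day ceiling reach?** Section 4.1.9 times EOT from treatment discontinuation; note 25 times it from the last dose. For an infusion-day stop the two agree. Appendix 12.3, which grades these reactions, also includes serum sickness at about 6 to 21 days. Timed from discontinuation, the longest intervals are then:
- stop on day 6: 28 + 6 + 30 = 64 days;
- stop on day 21: 28 + 21 + 30 = 79 days.

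Both exceed 63, so the EOT scan could be triggered. Timed from the last dose, the ceiling stays at 58.

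**4. What follows in the SAP?**
- SAP 4.1.3 requires a valid post-baseline assessment, or progression or death documented before any subsequent anticancer therapy. Without the 4.1.11 scans, the infusion-day patient may have none of these.
- SAP 4.9.4 and 4.9.5 estimate PFS and OS on that set, so such a patient would appear in neither. Duration of response is not involved, because no response was assessed.
- For a later stop, PFS (and duration of response in a responder) would be censored at the last valid assessment, and OS at the date last known alive.

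**5. Are the primary analyses exposed?** No. This reaction in Cycle 1 of Part 1 is itself a DLT (Protocol 6.3.1). The DLT-evaluable set drops early stoppers only when they had no DLT (Protocol 7.4), and SAP 4.1.2 keeps those with complete DLT information. AEs are collected for 12 weeks after the last dose or until new anticancer treatment (4.1.10, 6.3.2.2), and 4.2.2 follows the AE that caused the stop.

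**The case against.** The strongest reply is that the protocol already settles the matter. Section 4.2.1 is the dedicated withdrawal section and is mandatory in tone, while 5.2 concerns prophylaxis and is softer. Sections 3.1 and 4.1.11 cover a treatment stop for any reason except progression, which includes this one, so they need no cross-reference to apply. Section 4.2.2 itself speaks of a patient leaving the study because of an AE and still being followed, so the phrase is used loosely. To lose scans, a site must follow one clause against several others. This stands as to intent. It does not remove the conflicting instruction, because nothing says that the phrase in 5.2 means study drug only.

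It can also be said that SAP 4.9.4 censors patients without a post-baseline assessment on Day 1 and so keeps them in PFS. That rule works only within the efficacy set and does not bring in a patient who is outside it.

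A reader might infer more than the documents support:

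- *That follow-up is planned to end for these patients.* Sections 3.1, 4.1.11 and 4.2 say otherwise.
- *That a set number of scans or calls would be lost.* Any count has to assume that study exit cancels 4.1.11 yet leaves the 12-week visit intact. It must also assume call dates, although calls begin only after progression or new treatment and only the 12-month limit runs from the last dose.
- *That every Cycle 1 reaction ends in exclusion.* The window result holds for an infusion-day reaction and stop. A delayed reaction may trigger the EOT scan.

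**Conclusion.** The rule in 5.2 is wrong as written, and the matter is minor. The wording conflict with 4.2.1 is certain; the loss of data is conditional on a site reading 5.2, or the first rule of 5.4, literally. In the infusion-day case the result could be absence from the PFS and OS analyses; for a later stop, early censoring. The infusion-day result assumes that the 4.1.11 scans do not take place and that neither progression nor death is documented before new anticancer therapy.

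The endpoints concerned are secondary and descriptive, and SAP section 4 plans no hypothesis tests. The documents give no rate of Grade 3 or higher hypersensitivity, so neither the number of patients affected nor the size of any bias can be stated.

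**What to change.** In 5.2, replace the study-exit wording with *permanently discontinued from ADCT-402*, and add that follow-up under 4.1.9 to 4.1.11 continues to apply. Make the same replacement in the first rule of 5.4 for consistency. Leave the clinical stopping criteria as they are.

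The cost is two wording changes and one cross-reference. No procedure is added, since the follow-up is already planned.

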5.3 Treatments Administered

In Part 1 (dose escalation), each patient will be assigned a dose level and schedule as described in [Section 3.1](#) and [Section 3.2](#). In Part 2 (expansion), all patients will be assigned to the recommended dose level(s) and schedule(s) of ADCT-402 identified in Part 1 by the DESC.

ADCT-402 will be administered on Day 1 of each cycle as a 1-hour IV infusion. If ADCT-402 is well tolerated after the first cycle, the infusion duration may be shortened to 30 minutes for subsequent cycles, on an individual patient basis, at the Investigator's discretion. Variations in infusion times due to minor differences in IV bag overfill/underfill and the institution's procedure for flushing chemotherapy lines will not result in protocol deviation.

Prophylactic antiemetic medications, electrolyte supplementation, and other standard supportive care measures may also be administered according to standard treatment center protocols, or as in [Section 5.2](#) and [Section 5.9.2](#).

Although the study patient population has a low risk for development of tumor lysis syndrome (TLS) compared to patients with acute disease ([Cairo, 2010](#)), patients should be observed for development of TLS and treated according to standard treatment center protocols.

Because of non-clinical observations related to nephropathy, adequate patient hydration (e.g., 8 to 10 glasses of water or equivalent per day) is recommended for patients receiving ADCT-402.

Additionally, because new or worsening edema and / or new or worsening pleural effusion have been observed, patients are advised to monitor their weight on a daily basis ([Section 6.3.8](#) and [5.9.2](#))

As non-clinical testing indicates testicular toxicity (atrophy with reduced spermatogenesis), male patients are advised to consider cryopreservation of sperm prior to treatment with ADCT-402, where applicable.

Available pre-clinical data on ADCT-402 does not suggest a photosensitivity concern, based on the lack of any signals in the rat and monkey toxicology studies with ADCT-40

However, skin rash has been reported in the ADTC 402-101 study, as well as with another investigational agent containing the same pyrrollobenzodiazepine warhead (Rudin, 2016). The rash has been limited to areas at risk for sun exposure, it is therefore recommended that precautions are taken to avoid prolonged exposure of skin to direct sunlight.

